### **6.3. PROCEDURES FOR ELICITING REPORTS OF AND FOR RECORDING AND REPORTING ADVERSE EVENT AND INTERCURRENT ILLNESSES**

For any reported side effect: While with the participant, study personnel will listen, identify, and document the symptoms. All events will be documented on AE forms.

#### **6.3.A. OTHER EVENTS**

- Any participant who voices current suicidality or is experiencing a psychiatric emergency during the interview will be reported to [name] or his designee immediately. [name] and the assessor (Addiction Psychiatrist at City Addiction Hospital or at Pavlov University) will determine the appropriate course of action, which will depend on location of the event and the clinical situation. Emergency psychiatric consultation is available on site at the CAH and will be requested as indicated; patients will be escorted to receive care by appropriate staff if deemed necessary.

#### **6.3. B. ADVERSE EVENT REPORTING**

The following information should be present to complete AE and SAE forms during the initial report (on the day of finding out about the event):

- Description of the event
- Date of onset and resolution (if known)

- Severity – based on established criteria: [https://evs.nci.nih.gov/ftp1/CTCAE/CTCAE\\_4.03\\_2010-06-14\\_QuickReference\\_5x7.pdf](https://evs.nci.nih.gov/ftp1/CTCAE/CTCAE_4.03_2010-06-14_QuickReference_5x7.pdf) \* See Box 1

### **Box 1. Guidelines for Severity Grades**

\*Research assessor will refer to the guide for unique clinical descriptions of severity for each AE, which will follow the general guideline below:

- Grade 1 Mild; asymptomatic or mild symptoms; clinical or diagnostic observations only intervention not indicated.
- Grade 2 Moderate; minimal, local or noninvasive intervention indicated; limiting age-appropriate instrumental activities ADL\*.
- Grade 3 Severe or medically significant but not immediately life-threatening; hospitalization or prolongation of hospitalization indicated; disabling; limiting self care ADL\*\*.
- Grade 4 Life-threatening consequences; urgent intervention indicated.
- Grade 5 Death related to AE.

Not all Grades are appropriate for all AEs. Therefore, some AEs are listed with fewer than five options for Grade selection. Grade 5 (Death) is not appropriate for some AEs and therefore is not an option.

### **Activities of Daily Living (ADL)**

\*Instrumental ADL refer to preparing meals, shopping for groceries or clothes, using the telephone, managing money, etc.

\*\*Self care ADL refer to bathing, dressing and undressing, feeding self, using the toilet, taking medications, and not bedridden.

- Assessment of expectedness (is the event anticipated in terms of nature, severity, or frequency) given (a) the research procedures that are described in the IRB protocol and informed consent document; and (b) the characteristics of the subject population being studied
- Assessment of relatedness to Naltrexone
- Any actions taken

Following the initial report, additional information may need to be gathered to complete the AE and SAE forms and to evaluate the event for relatedness. This process may include seeking hospital discharge reports, physician records, autopsy records or any other type of records or information necessary to provide a complete and clear picture of the SAE and events preceding and following the event.

#### **6.3.C. SAE REPORTING**

If the SAE is not resolved or stabilized at this time or new information becomes available after the SAE form is completed, the SAE form should be updated as soon as possible. Any changes or updates to the SAE form will need to be re-reviewed and re-authorized by the study clinician.

In some cases, the study clinician may be unsure upon first learning of an SAE whether it is study related and/or expected, because study staff are awaiting more complete medical records. In such cases, the study clinician should make his/her best estimate of relatedness and expectedness, understanding that these determinations can be updated later. When updating determinations at a later date, the rationale for the change should be included in the SAE narrative.

The site must actively seek information about the SAE until the SAE is resolved, stabilized or until the participant is lost to follow-up and terminated from the study.

To summarize: upon determining an Adverse Event is Serious, the following procedures should be followed:

- The study staff, while meeting/talking with the participant or person providing details on the event, will gather as much information about the event from these individuals as possible and complete the appropriate forms.
- The completed AE and SAE forms will be reviewed by key personnel on the Pavlov team (e.g. Drs. [name] or [name]). Any relevant clinical documents (labs, physician notes) available at that time will be provided to key personnel on the Pavlov team (e.g. Drs. [name] or [name]) within 24 hours of finding out about the event.
- After initial notification, the SAE must be updated with any additional information.

Any Adverse Events will be entered on the study website and [name] will be alerted immediately of any SAEs or UPs.

### **BUMC Reporting Guidelines:**

The Principal Investigator at BMC/BU Medical Campus will report Unanticipated Problems and Adverse Events to the BMC/BU Medical Center IRB in accordance with IRB policies:

- Unanticipated Problems involving a fatal or life-threatening event will be reported to the IRB within 2 days of the investigator learning of the event.
- Unanticipated Problems not involving a fatal or life-threatening event will be reported to the IRB within 7 days of the investigator learning of the event.
- Adverse Events (including Serious Adverse Events) will be reported in summary at the time of continuing review, along with a statement that the pattern of adverse events, in total, does not suggest that the research places subjects or others at a greater risk of harm than was previously known.

### **Pavlov Reporting Guidelines:**

What Event is Reported	When is Event Reported
Fatal or life-threatening unexpected, suspected serious adverse reactions	Within 7 calendar days of initial receipt of information
Non-fatal, non-life-threatening unexpected, suspected serious adverse reactions	Within 15 calendar days of initial receipt of information

AEs and UPs	On a quarterly basis

#### **6.4 THE TYPE AND DURATION OF THE FOLLOW-UP OF SUBJECTS AFTER ADVERSE EVENTS**

All events will be followed until the event is resolved, stabilized, or until the end of individual's participation in the study.

Drs. [name] or [name] will determine a follow-up plan on a case-by-case basis based on their clinical judgment and this plan will be documented.

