#### **3.5.B. DISCONTINUATION OF STUDY MEDICATION**

Despite known side effects of naltrexone (both implant and injectable), most people taking the medications do not discontinue them due to side effects. Those who discontinue medication will be followed and analyzed by intention to treat.

Participants found to be pregnant during the study will have their study medication (i.e., naltrexone) discontinued (including removal of the implant if necessary), but will still be followed-up for the duration of the study. Participants who report pregnancy outside of study visits will be requested to come to Pavlov for a confirmatory pregnancy test where the need for implant removal will be assessed and the implant may be removed if deemed necessary.

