### 3.7.C. URINE

A pregnancy test will be administered by trained clinical research staff to all participants at screening and at each study visit for intervention participants. Pregnant women will be excluded from the study due to some reports suggesting possible adverse events with study medications. Participants found to be pregnant may have their implant removed but will still be followed-up for the duration of the study. For these participants the naltrexone implant will be removed (if removal is indicated) by clinical staff at Pavlov.

Urine will also be used to conduct urine drug testing on all intervention participants at all study visits and for control participants at the 6 and 12-month study visits. Urine drug tests must be negative for opioids before participants can receive the implant. Urine toxicology will test for a range of opioids, specifically opiates (products of the poppy plant – morphine, heroin, codeine) and synthetic opioids (specifically methadone). If new opioids appear on the scene in Russia, such as fentanyl, then we will begin testing for this, but currently that is not thought to be an issue.

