#### **Intervention Group:**

- At the **medication visits**, the Pavlov RA will perform the following:
  - Review and update locator/contact information, verifying new numbers, as necessary
  - Collect a urine sample to check for pregnancy and conduct drug testing
  - Collect clinical data (weight, blood pressure)
  - Assess opioid use
  - Perform symptom monitoring (including inspection of implant site) and brief counseling
  - Compensate participant and schedule next visit
- In addition to the above, at the **implant visits**, the Pavlov RA will perform the following:
  - Administer naloxone challenge
  - Provide naltrexone implant
  - Implant visits 2, 3, and 4: send participant for phlebotomy to check ALT/AST levels
- During the **24-, and 52-week assessments**, in addition to the medication visit procedures described above, the Pavlov RA will:
  - Send participant for phlebotomy (CD4, HVL)
  - Administer assessment questionnaire
  - **Subset of all participants:** In-depth interview

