### 6.1. SPECIFICATION OF SAFETY PARAMETERS

An **Adverse Event (AE)** is defined as any untoward or unfavorable medical occurrence in a human subject, including any abnormal sign (for example, abnormal physical exam or laboratory finding), symptom, or disease, temporally associated with the subject's participation in the research, whether or not considered related to the subject's participation in the research.

An AE can therefore be any new sign, reaction, symptom, event, disease or a worsening in frequency or severity of a preexisting condition that occurs during the course of the study.

*Stable chronic conditions that were present prior to study entry and do not worsen are not considered AEs.*

**SERIOUS Adverse Event (SAE)** – is any adverse event that

- (1) results in death;
- (2) is life-threatening;
- (3) results in inpatient hospitalization or prolongation of existing hospitalization;
- (4) results in a persistent or significant disability/incapacity;
- (5) results in a congenital anomaly/birth defect; or
- (6) based upon appropriate medical judgment, may jeopardize the subject's health and may require medical or surgical intervention to prevent one of the other outcomes listed in this definition (examples of such events include allergic bronchospasm requiring intensive treatment in the emergency room or at home, blood dyscrasias or convulsions that do not result in inpatient hospitalization, or the development of drug dependency or drug abuse).

Life-threatening means that the event places the subject at immediate risk of death from the event as it occurred.

**Unanticipated Problem (UP)** – is defined as an event, experience or outcome that meets all three of the following criteria:

- is unexpected; AND
- is related or possibly related to participation in the research; AND
- suggests that the research places subjects or others at a greater risk of harm (including physical, psychological, economic, or social harm) than was previously known or recognized.

Possibly related means there is a reasonable possibility that the incident, experience, or outcome may have been caused by the procedures involved in the research

Unexpected means the nature, severity, or frequency of the event is not consistent with either:

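### Nothing requires the outcome of a pregnancy still ongoing at the last visit to be sought after naltrexone exposure, although a birth defect is on the plan's own SAE list

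*Combined protocol and SAP*

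**What the plan says.** **Pregnancy.** Section 2.7 excludes women who are pregnant, planning pregnancy or breastfeeding at entry. Section 3.7.C gives the reason: "Pregnant women will be excluded from the study due to some reports suggesting possible adverse events with study medications". Intervention participants are retested during follow-up; the medication-visit procedures in section 4.4 include "Collect a urine sample to check for pregnancy and conduct drug testing". Under section 3.5.B, a participant who becomes pregnant has her naltrexone "discontinued (including removal of the implant if necessary), but will still be followed-up for the duration of the study". Section 3.7.C says the same: "Participants found to be pregnant may have their implant removed but will still be followed-up for the duration of the study". Section 3.5.B also asks women who report a pregnancy between visits to come in for a confirmatory test.

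**Safety events.** The fifth SAE criterion in section 6.1 is an event that "results in a congenital anomaly/birth defect". For the length of follow-up, section 6.4 says: "All events will be followed until the event is resolved, stabilized, or until the end of individual's participation in the study". It adds that named clinicians "will determine a follow-up plan on a case-by-case basis based on their clinical judgment and this plan will be documented". For SAEs, section 6.3.C says the site "must actively seek information about the SAE until the SAE is resolved, stabilized or until the participant is lost to follow-up" and has been terminated from the study. Section 6.2 requires an event discovered outside scheduled visits to be recorded all the same.

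**The concern.** The plan treats possible harm in pregnancy seriously enough to exclude pregnant women, retest the exposed arm and stop the drug. The outcome that would show such harm is a birth defect, and it usually becomes known only at or after delivery. The follow-up rules end earlier than that for many of the pregnancies that could occur.

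At stake is an individual safety record. Staff could follow every instruction and still not learn of an SAE that the plan itself names. The primary and secondary efficacy analyses are not touched.

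**Working it through.** The plan states no figure on this point to reproduce. The check compares the provisions and then works out timing.

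**1. Does any provision reach an outcome after the last visit?**

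| Provision | What it covers | Does it require the outcome to be sought? |
|---|---|---|
| 3.5.B, 3.7.C | The pregnant participant, for the study's duration | No; delivery, loss and infant are not mentioned |
| 6.4, first sentence | Events, to the end of individual participation at most | No; also silent on whether a pregnancy is an event |
| 6.4, second sentence | A documented plan set by clinicians case by case | Permitted, not required; no minimum length |
| 6.3.C | An SAE that already exists | No; an ongoing pregnancy is not on the SAE list |
| 6.2 | Events discovered outside visits | Recording is required, searching is not |
| 3.7.D | Chart review of HIV and addiction care, to 12 months | No |
| 3.6, 5.2, 7.4 (schedules, assessments, forms) | Scheduled contacts and forms | No pregnancy-outcome form, later contact or infant assessment |

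The 12-month reproductive-health items (section 5.2) cannot capture a later delivery. The AE definition in section 6.1 refers to occurrences in the course of the study, so a finding after participation may not clearly count as an AE.

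**2. Which pregnancies are undelivered at the last visit?**

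Inputs: visit at week 52, or at the day 455 window close (section 3.6.A), which is 455/7 = 65 weeks; implants ideally at weeks 4, 16, 28 and 40 (section 2.4). Assumption, not in the documents: 38 weeks from conception to birth, range 37-40.

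Latest conception week that delivers before the visit = visit week − 38.

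- Week 52: 52 − 38 = 14 (range 12-15). The implants at weeks 16, 28 and 40 fall later, three of four.
- Week 65: 65 − 38 = 27 (range 25-28). The week-40 implant falls later throughout; the week-28 implant falls at or just after the cut-off.

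Example: a first positive test at week 52 after a negative test at week 48, assuming tests turn positive about 2 weeks after conception. Conception falls in weeks 46-50, which is 6-10 weeks after a week-40 implant and inside the 10-12 week implant interval. Birth falls in weeks 84-88, which is 32-36 weeks after the visit.

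**3. What share of births is affected?**

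Further assumption: conceptions even over weeks 0-52.

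- *If duration means the individual's participation:* 38/52 = 73% of births come after a week-52 visit.
- *If duration means the whole trial:* accrual is 30 months (section 2.8), assumed even, or 30 × 4.348 = 130.4 weeks. Births in ongoing pregnancies come 0-38 weeks after the mother's visit, mean 19.
  - Trial ends with the last participant's visit at week 52: 19/130.4 = 14.6% of those births fall outside; 0.731 × 14.6% = 11% of all births.
  - Last participant's visit at week 65, 13 weeks later: mean excess = (38 − 13)²/(2 × 38) = 8.22 weeks; 8.22/130.4 = 6.3%; 0.731 × 6.3% = 5% of all births.

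All of these are shares of an unknown number of pregnancies.

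**The case against.** The best reply is that the plan already has the needed pieces. Clinicians set and document an individual follow-up plan with no stated end date. Section 6.3.B provides for obtaining hospital and physician records. Any event that comes to light must be recorded, and an SAE recognised before the last visit must be pursued. Pregnancy and planned pregnancy are excluded at entry, the exposed arm is retested and naltrexone is stopped, so cases will be few. Consent wording may also cover the matter.

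Most of this stands, and it limits the point. A reader might infer that a birth defect would go unrecorded even if staff heard of it. Section 6.2 rules that out; what is missing is a duty to ask. A reader might also take 73% as the share of outcomes lost. It applies only on the narrower reading of study duration, and on the wider one the comparable figure is 5-11%. The concern does not extend to controls either: the plan gives them no naltrexone, so their pregnancies carry no information about this exposure.

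The reply does not supply a requirement. Discretion permits ascertainment without ensuring it. Section 6.4 uses the individual's participation as its limit, and neither reading of study duration names delivery or the infant. The consent pages are not in the text reviewed, so a clause there can be neither confirmed nor excluded.

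**Conclusion.** The point holds as a gap in safety ascertainment that is cheap to close. For a woman who received naltrexone and is still pregnant at her last visit, the plan allows the outcome to be sought but does not require it, and an SAE named in section 6.1 can be missed with full adherence.

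The timing result rests on 38 weeks to birth: conceptions after about week 14 are undelivered at week 52. The shares rest also on even conceptions and, for the whole-trial reading, even accrual. The absolute number cannot be estimated because the documents give no pregnancy rate; given the entry exclusions it is probably very small. Nothing here shows that naltrexone causes birth defects or that one has been missed, and no efficacy conclusion changes.

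**What to change.** State in sections 3.5.B, 3.7.C and 6.4:

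> Any pregnancy in a participant who received naltrexone is followed, with her consent, to its outcome (live birth, loss or termination, and any birth defect), even after the 12-month visit. Existing research staff obtain the outcome by phone or record; it is listed individually, and an AE/SAE form is completed when the outcome is adverse.

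This needs no new visits or tests. Section 4.7 already has contact details for the participant and her alternative contacts updated at each visit, and the AE/SAE form exists (section 7.4). A normal live birth is listed but does not go on that form.

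Cost: protocol and consent wording, re-consent of any already enrolled participant affected, and a few calls. A few safety records would be entered up to about 38 weeks after the last visit. The efficacy analysis does not wait for them.

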### **7. DATA MANAGEMENT**

#### **7.1 DATA COLLECTION**

All study data will be captured electronically on netbooks via a secure, web-based data capture system.

#### **7.2 QUALITY CONTROL PROCESS**

Quality control measures will include: detailed and unambiguous specifications for completion of data forms, including rules for coding skipped questions and missing data, training of study staff responsible for data collection and built-in validation rules, error checks, question skips for electronic data capture, and computer algorithms to check for out-of-range codes and internal inconsistencies. All data, regardless of capture method, will be converted to SAS datasets and reviewed for logic, skip patterns, response ranges, out-of-range codes, and internal inconsistencies. The RAs will be queried regarding any noted inconsistencies.

#### **7.3 DATA SECURITY AND CONFIDENTIALITY**

Screening forms and most other research paperwork will not include the participant's name; instead, a unique ID will be assigned to each person screened, and another number assigned to those who enrolled. Any documents with identifiable participant data will only be accessible to the Russian Co-Investigators (Drs. [name] and [name]), the project management staff, and the RAs who recruit and follow participants.

Tracking information will be kept similarly. Computer data will be password protected, and accessible only to research associates needing the information for follow-up purposes.

The Boston University Biostatistics & Epidemiology Data Analytics Center (BEDAC) will design, develop and maintain the electronic data collection forms, participant and data tracking, and underlying SQL database systems, and implement procedures for data quality control, including multiple checks for entered data. Electronic data collection forms will be designed to read easily, have clear instructions, preprogrammed skip patterns, real-time range checks and internal logic to minimize missing data and result in "cleaner" data at capture. The website and accompanying database will be located on secure, password-protected servers, behind the BU firewalls. The BEDAC has access to two Unix servers, including a Linux Beowulf cluster currently configured with 118 CPUs, as well as an SMP Linux server with 4 x Six-Core AMD Opteron processors (a total of 24 cores x 2.4 GHz each), 64 GB of RAM, and 6 TB (4TB usable) storage capacity. Additionally, the BEDAC has three dedicated servers, all of which are dual processors with 150 gigabytes for data storage: an SQL database server; a server used for Web site development and management, running Internet Information Server for web page hosting; and a server used for web development pre-production testing environment. The web and database servers will use Secure Socket Layering (SSL) to ensure data security and confidentiality. Two fax servers, an additional server, and a flatbed scanner comprise the Teleform® system. Servers incorporate RAID hard drives for data redundancy. A separate web server dedicated for Cold Fusion applications is also available.

The in-depth qualitative interviews will be recorded, and the clinician's or patient's name could be mentioned or their identity could otherwise be revealed during the interview; however sensitive information will not be the content of the interviews. Names will not be transcribed and audiorecordings will be destroyed after transcription. The audiorecordings will be kept in a locked cabinet when not in use.

